## 9.3.1.2 Exclusion Criteria

Subjects will be ineligible for trial participation if they meet **any** of the following criteria:

- 1. Any of the following cardiovascular diseases:
  - a. uncontrolled, severe hypertension (≥160/100 mmHg), within 6 months of Screening
  - b. myocardial infarction within 6 months of Screening
  - c. unstable cardiac angina within 6 months of Screening
- 2. ILD associated with known primary diseases (e.g., sarcoidosis, amyloidosis, and coronavirus disease 2019 [COVID-19]), connective tissue disorders (e.g., rheumatoid arthritis, systemic lupus erythematosus, Sjogren's, dermatomyositis, scleroderma), exposures (e.g., radiation, silica, asbestos, and coal dust) or drugs (e.g., amiodarone).
- 3. Known active bacterial, viral, fungal, mycobacterial, or other infection, including tuberculosis or atypical mycobacterial disease (fungal infections of nail beds are allowed). The subject must be 3 months beyond any acute infection with COVID-19 if there has been a prior infection.
- 4. Clinically significant pulmonary hypertension requiring chronic medical therapy.
- 5. Use of any of the following therapies within 4 weeks prior to Screening, during the Screening Period or planned during the trial: prednisone at steady dose >10 mg/day or equivalent or cyclosporine. Change in regimen or dosage of any immunosuppressant during the Screening Period through the end of trial participation will require consultation with and approval by the trial Medical Monitor. See Section 9.4.9 for full details. Avoiding the use of listed prohibited treatments must not be considered detrimental and must be indicated by the treating physician. Subjects must not be withdrawn from any standard-of-care treatment that is considered necessary for the clinical management of the subject in order to fulfill the trial eligibility requirements.
- 6. Use of rifampin within 2 weeks prior to Day 1 or planned during the trial.
- 7. Malignant condition in the past 5 years (except successfully treated basal/squamous cell carcinoma of the skin or cervical cancer in situ).
- 8. Women of childbearing potential (WOCBP) or male subjects not agreeing to use highly effective method(s) of birth control throughout the trial and for 4 weeks after last dose of trial drug. Females must refrain from egg/ova donation for 4 weeks after the last dose of trial drug and males must refrain from sperm donation for 3 months after the last dose of trial drug. Women are considered of childbearing potential if they are not postmenopausal and not surgically sterile (documented bilateral salpingectomy, bilateral oophorectomy, or hysterectomy). A postmenopausal state is defined as no menses for 12 months without an alternative medical cause. A high follicle-stimulating hormone (FSH) level in the postmenopausal range may be used to confirm a postmenopausal state in women not using hormonal contraception or hormonal replacement therapy. However, in the absence of 12 months of amenorrhea, a single FSH measurement is insufficient. Fertile male subjects must use a condom throughout the trial and for 4 weeks after the last

Fipaxalparant (HZN-825) Protocol: HZNP-HZN-825-303 Version 5.0, Amendment 4

- dose of trial drug. A man is considered fertile after puberty unless permanently sterile by bilateral orchidectomy.
- 9. Pregnant or lactating women and women who plan to become pregnant or breast feed during the trial and within 4 weeks after the last dose of trial drug.
- 10. Current drug or alcohol abuse or history of either within the previous 2 years, in the opinion of the Investigator or as reported by the subject.
- 11. Previous enrollment in this trial or participation in a prior fipaxalparant (HZN-825) or SAR100842 clinical trial.
- 12. Known history of positive test for human immunodeficiency virus (HIV). HIV testing is optional based on Investigator assessment, institutional practices or local guidelines, to rule out suspected HIV or potential for a positive HIV result. Subject consent is required prior to HIV testing.
- 13. Active hepatitis (any of the following at Screening):

# *Hepatitis B*:

- positive hepatitis B surface antigen
- positive for anti-hepatitis B core antibody (anti-HBcAb) and a positive test for hepatitis B surface antibody (HBsAb) and presence of hepatitis B virus DNA
- positive for HBcAb and a negative test for HBsAb and presence of hepatitis B virus DNA

## Hepatitis C:

- positive anti-hepatitis C virus (anti-HCV) and positive HCV RNA.
- 14. Current alcoholic liver disease, primary biliary cirrhosis or primary sclerosing cholangitis.
- 15. Previous organ transplant (including allogeneic and autologous marrow transplant).
- 16. INR >2, prolonged prothrombin time >1.5  $\times$  the upper limit of normal (ULN) or partial thromboplastin time >1.5  $\times$  ULN at Screening.
- 17. Alanine aminotransferase (ALT) or aspartate aminotransferase (AST) >2.0 × ULN.
- 18. Estimated glomerular filtration rate <30 mL/min/1.73 m^2 at Screening.
- 19. Total bilirubin >1.5  $\times$  ULN. Subjects with documented diagnosis of Gilbert's syndrome may be enrolled if their total bilirubin is  $\leq$ 3.0 mg/dL.
- 20. Moderate (Child-Pugh B) to severe (Child-Pugh C) hepatic impairment according to the Child-Pugh scoring system.
- 21. Any confirmed Grade 3 or higher laboratory abnormality.
- 22. Any laboratory abnormality at Screening that, in the opinion of the Investigator, would preclude the subject's participation in the trial.
- 23. Exposure to an experimental drug or experimental vaccine within either 30 days, 5 half-lives of the test agent, or twice the duration of the biological effect of the test agent, whichever is the longest, prior to Day 1.
- 24. Any other condition that, in the opinion of the Investigator, would preclude enrollment in the trial.

## 9.3.2 Eligibility Criteria for the Extension Phase

## 9.3.2.1 Inclusion Criteria

Eligible subjects must meet/provide all of the following criteria:

- 1. Written informed consent.
- 2. Completed the Double-blind Treatment Period (Week 52) of the Core Phase of the trial; subjects prematurely discontinued from trial drug in the Core Phase of the trial for reasons other than safety or tolerability may be included at the discretion of the Investigator after completing scheduled visits, including Week 52 assessments.
- 3. Willing and able to comply with the prescribed treatment protocol and evaluations for the duration of the Extension Phase of the trial.

#### 9.3.2.2 Exclusion Criteria

Subjects will be ineligible for trial participation if they meet any of the following criteria:

- 1. Anticipated use of another investigational agent for any condition during the course of the trial.
- 2. New diagnosis of malignant condition after enrolling in Trial HZNP-HZN-825-303 (except successfully treated basal/squamous cell carcinoma of the skin or cervical cancer in situ).
- 3. Estimated minimum life expectancy  $\leq$ 18 months, in the opinion of the Investigator.
- 4. WOCBP or male subjects not agreeing to use highly effective method(s) of birth control throughout the trial and for 1 month after last dose of fipaxalparant (HZN-825). Male subjects must refrain from sperm donation and females from egg/ova donation for this same time period. Women are considered of childbearing potential if they are not postmenopausal and not surgically sterile (documented bilateral salpingectomy, bilateral oophorectomy, or hysterectomy). A postmenopausal state is defined as no menses for 12 months without an alternative medical cause. A high FSH level in the postmenopausal range may be used to confirm a postmenopausal state in women not using hormonal contraception or hormonal replacement therapy. However, in the absence of 12 months of amenorrhea, a single FSH measurement is insufficient. A man is considered fertile after puberty unless permanently sterile by bilateral orchidectomy.
- 5. Pregnant or lactating women.
- 6. Any other new development of the disease/condition/significant laboratory test abnormality during the course of the Core Phase of the trial, in the opinion of the Investigator, that would potentially put the subject at unacceptable risk.
- 7. In the opinion of the Investigator, unlikely to comply with the trial protocol or has a concomitant disease or condition that could interfere with the conduct of the trial.

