## **Exclusion Criteria:**

Subjects will be ineligible for Extension Phase of the study if they meet any of the following criteria:

- 1. Anticipated use of another investigational agent for any condition during the course of the trial.
- 2. New diagnosis of malignant condition after enrolling in Trial HZNP-HZN-825-303 (except successfully treated basal/squamous cell carcinoma of the skin or cervical cancer in situ).
- 3. Estimated minimum life expectancy ≤18 months, in the opinion of the Investigator.
- 4. WOCBP or male subjects not agreeing to use highly effective method(s) of birth control throughout the Extension Phase and for 4 weeks after last dose of fipaxalparant (HZN-825). Females must refrain from egg/ova donation for 4 weeks after the last dose of trial drug and males must refrain from sperm donation for 3 months after the last dose of trial drug. Women are considered of childbearing potential if they are not postmenopausal and not surgically sterile (documented bilateral salpingectomy, bilateral oophorectomy, or hysterectomy). A postmenopausal state is defined as no menses for 12 months without an alternative medical cause. A high FSH level in the postmenopausal range may be used to confirm a postmenopausal state in women not using hormonal contraception or hormonal replacement therapy. However, in the absence of 12 months of amenorrhea, a single FSH measurement is insufficient. A man is considered fertile after puberty unless permanently sterile by bilateral orchidectomy.
- 5. Pregnant or lactating women.
- 6. Any other new development of the disease/condition/significant laboratory test abnormality during the course of the Core Phase of the trial, in the opinion of the Investigator, that would potentially put the subject at unacceptable risk.
- 7. In the opinion of the Investigator, unlikely to comply with the trial protocol or has a concomitant disease or condition that could interfere with the conduct of the trial.

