# 5.3 Subject Information and Consent

It is the responsibility of the Investigator, or a person designated by the Investigator (if acceptable by local regulations) to obtain signed informed consent from each subject prior to participating in this trial after adequate explanation of the aims, methods, anticipated benefits and potential hazards of the trial. Both the Core Phase and the optional open-label extension (OLE) Phase will require separate ICFs to be signed by subjects.

The Investigator or designee must also explain that the subjects are completely free to refuse to enter the trial or to withdraw from it at any time, for any reason.

The ICF and any other written information provided to subjects will be revised whenever important new information becomes available that may be relevant to the subject's consent, or there is an amendment to the protocol that necessitates a change to the content of the subject information and/or the written ICF. The Investigator will inform the subject of changes in a

PRIVATE AND CONFIDENTIAL INFORMATION OF HORIZON THERAPEUTICS IRELAND DAC (A WHOLLY OWNED SUBSIDIARY OF AMGEN INC.)

Page 47 of 153

Fipaxalparant (HZN-825) Protocol: HZNP-HZN-825-303 Version 5.0, Amendment 4

timely manner and will ask the subject to confirm his/her participation in the trial by signing the revised ICF. Any revised written ICF and written information must receive the external review bodies' approval/favorable opinion in advance of use.

All signed ICFs are to remain in the Investigator's site file or, if locally required, in the subjects' notes/files of the medical institution.

The electronic case report forms (eCRFs) for this trial contain a section for documenting all subject informed consent(s) and this must be completed appropriately. If new safety information results in significant changes in the risk/benefit assessment, the ICF should be reviewed and updated if necessary. All subjects (including those already being treated) should be informed of the new information, given a copy of the revised form and give their consent to continue in the trial.

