#### BID=twice daily

- 1. The fipaxalparant (HZN-825) dose may be modified based on the results of the Core Phase.
- 2. If a subject prematurely discontinues open-label fipaxalparant (HZN-825), he/she will be asked to remain in the trial, participating in the scheduled trial visits through Week 104. If a subject prematurely discontinues open-label fipaxalparant (HZN-825) and does not wish to continue in the trial, he/she will be asked to return for a clinic visit and undergo the Week 104 assessments.
- 3. Visit windows are ±5 days for Week 56, ±7 days for Week 62 to Week 104, inclusive, and ±14 days for the Safety Follow-up Visit.
- 4. Visits at Weeks 74, 86, and 98 are remote (telephone) visits with a  $\pm$ 7-day window.

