## 9.3.3 Removal of Subjects from Treatment or the Trial

All subjects are free to withdraw from trial participation at any time, for any reason and without prejudice to their further medical care. In addition, the Investigator may terminate a subject from treatment at any time, if further treatment in the trial is not in the best interest of the subject.

If a subject prematurely discontinues trial drug, he/she will be asked to remain in the trial, participating in the scheduled trial visits through Week 52 (if discontinuation occurs during the Core Phase) or Week 104 (if discontinuation occurs during the Extension Phase). If a subject prematurely discontinues trial drug and does not wish to continue in the trial, he/she will be asked to return for a clinic visit and undergo the Week 52 (if discontinuation occurs during the Core Phase) or Week 104 (if discontinuation occurs during the Extension Phase) assessments. Subjects will be asked to return to the clinic for a Safety Follow-up Visit 4 weeks after the last dose of fipaxalparant (HZN-825).

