### 9.5.5.2 Pregnancy and Lactation Reporting

Pregnancy testing will be performed for WOCBP. Serum pregnancy tests will be analyzed at a central trial laboratory and the urine pregnancy tests will be performed locally. In addition, at-home pregnancy tests will be completed by WOCBP at Weeks 8, 12, 20, 24, 32, 36, 44, and 48 during the Core Phase and at Weeks 60, 64, 72, 76, 84, 88, 96 and 100 during the Extension Phase, and results will be reported to the site.

If a female subject becomes pregnant during the Double-blind Treatment Period, she should immediately notify the Investigator and trial drug dosing should be permanently discontinued but the subject will be asked to continue in the trial for evaluations.

Pregnancy occurring in the partner of a male subject participating in the trial should be reported to the Investigator and the Sponsor immediately upon awareness of pregnancy. Monitoring of the subject's partner should continue until conclusion of the pregnancy.

Subjects should be instructed to continue contraception for 4 weeks after their last dose of trial drug. Pregnancies occurring up to 4 weeks after the last dose of trial drug must also be reported to the Investigator.

Some examples of highly effective contraceptive methods that have a failure rate of <1% per year when used consistently and correctly are:

- Combined (estrogen- and progestogen-containing) hormonal contraception associated with inhibition of ovulation
  - o Oral
  - Intravaginal
  - Transdermal
- Progestogen-only hormonal contraception associated with inhibition of ovulation
  - o Oral
  - o Injectable
  - o Implantable
- Intrauterine device
- Intrauterine hormone-releasing system
- Bilateral tubal ligation
- Vasectomized partner
- Sexual abstinence from heterosexual intercourse

There are no expected drug interactions between fipaxalparant (HZN-825) and hormonal contraceptives.

Abstinence should only be used as a contraceptive method if it is in line with the subject's usual and preferred lifestyle. Periodic abstinence (calendar, symptothermal, postovulation methods) is not an acceptable method of contraception.

Details of all pregnancies and/or lactation in female subjects and pregnancies in female partners of male subjects will be collected after the start of study treatment and until 4 weeks after last dose of trial drug.

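### Extension Phase exclusion criterion 4 sets two different sperm-donation periods after the last dose: 3 months in the synopsis, 1 month in Section 9.3.2.2

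*Protocol*

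**What the plan says.** Extension Phase exclusion criterion 4 appears in two places in the current protocol.

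- **Synopsis, Extension Phase exclusion criteria.** Contraception is required "throughout the Extension Phase and for 4 weeks after last dose of fipaxalparant (HZN-825"). Egg or ova donation is barred for 4 weeks after the last dose. For men, "males must refrain from sperm donation for 3 months after the last dose of trial drug".
- **Section 9.3.2.2.** Contraception is required "throughout the trial and for 1 month after last dose of fipaxalparant (HZN-825"). The next sentence is "Male subjects must refrain from sperm donation and females from egg/ova donation for this same time period". Sperm and egg donation therefore both take the 1-month period.

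Four other parts of the protocol bear on the point.

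- Core Phase exclusion criterion 8, in both the synopsis and Section 9.3.1.2, sets 4 weeks for contraception and egg donation and 3 months for sperm donation.
- Section 9.5.5.2 says "Subjects should be instructed to continue contraception for 4 weeks after their last dose of trial drug", but gives no sperm-donation period.
- Section 5.3 states that the Core and Extension Phases "will require separate ICFs to be signed by subjects".
- Section 7.1.3.5 lists embryo-fetal toxicity among the important potential risks. Section 7.1.3.2 reports no effect on fertility or early embryonic development in rats and no developmental toxicity in rats or rabbits.

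**The concern.** The two versions of the criterion cannot both be followed as written, and the protocol does not rank the synopsis against the body. The shorter sperm-donation period is in the detailed body section specific to the Extension, which a site could reasonably take as the working text. A man told 1 month would be free to donate while the synopsis, and the Core criterion he entered under, still bar it.

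Because the Extension has its own consent form, an error in the Extension criteria could have been copied into what participants are told. That form is not among the documents, so this is a possibility and not a finding.

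What is at stake is the accuracy and consistency of a reproductive-safety instruction. The trial's statistical conclusions do not depend on it.

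**Working it through.** The protocol offers no figure to reproduce here. The check is a side-by-side reading and a small calendar count.

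**Periods after the last dose, current text only**

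| Place | Contraception | Egg/ova donation | Sperm donation |
|---|---|---|---|
| Synopsis, Core criterion 8 | 4 weeks | 4 weeks | 3 months |
| Section 9.3.1.2, Core criterion 8 | 4 weeks | 4 weeks | 3 months |
| Synopsis, Extension criterion 4 | 4 weeks | 4 weeks | 3 months |
| Section 9.3.2.2, Extension criterion 4 | 1 month | 1 month | 1 month |
| Section 9.5.5.2 | 4 weeks | not stated | not stated |

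Three of the four eligibility statements give 3 months for sperm donation. Section 9.3.2.2 alone gives 1 month.

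**Size of the gap for sperm donation.** The difference is 3 months − 1 month = 2 calendar months. The shortest pair of consecutive months is February and March, 28 + 31 = 59 days. The longest is two 31-day months in a row (July and August, or December and January), 31 + 31 = 62 days. The restriction in Section 9.3.2.2 is therefore 59 to 62 days shorter.

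**Size of the gap for contraception and egg donation.** One month is 28 to 31 days and 4 weeks is 28 days. The difference is 28 − 28 = 0 to 31 − 28 = 3 days, with Section 9.3.2.2 the longer. This is immaterial.

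**Last scheduled contact.** Section 9.3.3 sets the "Safety Follow-up Visit 4 weeks after the last dose of fipaxalparant (HZN-825"), and the footnotes to Figure 9.2 allow ±"14 days for the Safety Follow-up Visit". The visit therefore falls on day 28 − 14 = 14 to day 28 + 14 = 42. Three months is 89 days (February to April, 28 + 31 + 30) to 92 days (for example July to September, 31 + 31 + 30). For a man who completes treatment, the 3-month period ends 89 − 42 = 47 to 92 − 14 = 78 days after that visit, so the instruction has to be right by then.

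**Where the 1-month text probably came from.** The amendment log is used here only for origin, since it describes superseded text. The donation sentence in Section 9.3.2.2 is the same as the one in Version 3.0 of Core criterion 8. Amendment 3 replaced that Core sentence with separate periods, including 3 months for sperm donation. The same amendment added the Extension criteria to both the synopsis and Section 9.3.2, so the two places were meant to match. A carry-over of the old Core wording is the likeliest explanation, although the protocol does not say so.

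**The case against.** The case for treating this as minor is strong on exposure.

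- **Few people affected.** Section 7.1.1 notes that IPF usually occurs after age 50. The affected group is men who would donate sperm between about 1 and 3 months after their last Extension dose. The documents give no number, and it may be near zero. This stands.
- **Reassuring animal data.** The findings in Section 7.1.3.2 are negative. This stands too, although Section 7.1.3.5 still lists embryo-fetal toxicity as an important potential risk.
- **Core criterion already covers it.** Every Extension participant entered under Core criterion 8, which runs from the last dose of trial drug. The synopsis counts up to 104 weeks of exposure to trial drug across both parts. Read literally, 3 months already applies after the last Extension dose, so the intended period is hardly in doubt. This lowers the risk but does not remove the contradiction, because Section 9.3.2.2 is the body text specific to the Extension.
- **The follow-up-visit argument is weak.** The 3-month period outlasts the last visit under the correct text as well, so the discrepancy does not cause that. The Extension also has clinic visits at Weeks 56, 62, 68, 80, 92 and 104, each a chance to give the right instruction. A man who stops drug early but keeps attending may have visits after his 3 months end. These points are right, and the conclusion does not depend on that argument.
- **The consent form is unseen.** It may already say 3 months, so it cannot be shown that any participant was told 1 month. This stands.

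None of this disputes that the two current texts differ or that one of them needs correcting.

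**Conclusion.** The inconsistency is real, and Section 9.3.2.2 is wrong as written. It shortens the sperm-donation restriction by 2 calendar months relative to the synopsis version of the same criterion and to both statements of the Core criterion.

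The reading that 3 months is intended rests on those three matching statements and on the inferred origin of the 1-month wording. If 1 month were in fact intended for the Extension, the synopsis would be wrong instead and a correction would still be needed.

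This is a drafting inconsistency in an eligibility condition and participant-safety instruction. Practical exposure is probably very small, and no efficacy or safety analysis changes. It should be corrected because it concerns reproductive risk and the correction is simple, not because harm has been shown.

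**What to change.** In Section 9.3.2.2, criterion 4, replace the periods with those in the synopsis: contraception throughout the Extension Phase and for 4 weeks after the last dose, no egg or ova donation for 4 weeks after the last dose, and no sperm donation for 3 months after the last dose. Then check that the Extension consent form states the same three periods.

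The cost is a one-sentence edit in the next amendment and one document check. A clarification letter to sites is needed only if the consent form says 1 month.
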